8.0 STATISTICAL METHODS

8.1 Sample Size

Aim 1 (Survey): A sample size of 1090 eligible subjects is required to address Specific Aim 1. We have chosen this sample size based on our preliminary study (Section 2.9), from which we can assume that 90% (n=981) of those approached will participate in the survey. A sample of 981 survey participants for Specific Aim 1 will provide 80% power to reject the null hypothesis that the prevalence (p) of HPV vaccine initiation is ≤ 0.4 if the true p is at least 0.44 (one-sided test, Type I error=0.05). It will also provide a 2-sided 95% confidence interval (CI) of sample $p \pm .061$ if true $p=0.4$.

[Protocol v3, 8/17/15: Accrual goal for Aim 1 met, enrollment to survey closed]

Aim 2 (Vaccine Evaluation):

qHPV Vaccine Cohort (patients enrolled on or before 3-1-16): Based on national vaccine initiation rates and our preliminary data (Section 2.9),⁴⁰ we conservatively assume that 60% (n=589) of the 981 survey participants will have not initiated the HPV vaccine. Based on our data (Section 2.9) and prior trials,^{30,31,135} we conservatively assume that of the non-vaccinated survey participants, 60% (n=353) will agree to receive the vaccine, 96% (n=339) will be seronegative at baseline (Intent to Treat [IT] sample), and 92% (n=312) will complete all 3 doses, yielding 312 (Per-Protocol [PP]) subjects who will have received all 3 doses of qHPV vaccine for examining Aim 2.1. This sample size was calculated using the mean GMT and SD reported by Merck & Co.²⁸ for healthy males and females aged 9-15 years and 16-26 years as the historical healthy population. The following assumptions were made: i) cancer survivors were similarly distributed in regard to immunogenicity with the same SD as in this healthy population; ii) margin of equivalence (E) was $\frac{1}{2}$ of the mean GMT of the healthy population (Table 7). Using the method of Korn and Freidlin¹³⁶ for sample size calculations using historical controls, a total of 312 subjects (72 younger females, 77 older females, 82 younger males, and 81 younger males) will provide 80% power to demonstrate non-inferiority with respect to anti-HPV-16, and/or -18 GMT in cancer survivors compared to the healthy population assuming a one-sided t-test, Type I error =0.00312 (for an overall Type I error =0.025), and margin of equivalence (E) shown in Table 7 by sex and age for each vaccine type.

Table 7. Sample Size for Aim 2 (Vaccine Evaluation)

		Females								

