Outcome measure: (seropositivity) [Exploratory only; study is not powered for this]: The percent of seropositive participants at Month 7 will be compared to the percent of age- and sex-matched seroconverted individuals in the historical healthy population for each of 2 vaccine components. Two one-sided tests of noninferiority (for each of 2 HPV types) will be conducted for each age-sex group at the 0.025 level (multiplicity adjusted) according to the methods of Miettinen and Nurminen.¹³⁷ Seroconversion in cancer survivors will be considered non-inferior if the lower 95% CI for the difference in percent seropositive between the healthy and cancer population is <5 percentage points.³⁰ The above analyses will be conducted for PP and IT samples. Although not powered to detect non-inferiority for HPV-6 and -11 (and in the 9vHPV cohort, HPV-31, -33, -45, -52, and -58), we will also conduct similar analyses for GMT and seropositivity for these types.

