Outcome measure (seropositivity): Seropositivity is defined as: qHPV cohort: Anti-HPV-6, -11, -16, and -18 titer $\geq 20, 16, 20,$ and 24 mMU/ml respectively;³⁰ 9vHPV cohort: Anti-HPV-6, -11, -16, -18, -31, -33, -45, -52, and -58 titer $\geq 30, 16, 20, 24, 10, 8, 8, 8,$ and 8 mMU/ml, respectively.⁶⁹ Among PP participants, the percent seropositive to each vaccine subtype will be computed and compared to age- and sex-matched seropositive rates at Month 24 in the healthy population.²⁸ One-sided tests of noninferiority for each HPV type will be conducted at the 0.025 (multiplicity adjusted) level according to the methods of Miettinen and Nurminen.¹³⁷ For each subtype and time point, persistence of seropositivity will be considered non-inferior in cancer survivors if the lower 95% CI for the difference in percent seropositivity between the healthy and cancer population is less than 5 percentage points. To identify factors associated with response persistence at each time point, we will classify cancer survivors as having impaired response persistence if their GMT is lower than $\frac{1}{2}$ of the mean GMT in the age-sex-time matched healthy population. Logistic regression will be conducted at each time point to identify significant predictors of impaired response persistence. Potential predictors include sex, primary diagnosis, current age, age at diagnosis/HCT, prior therapy (all therapeutic exposures, including cumulative doses of all immunosuppressive agents), intensity of therapy (conventional therapy vs. HCT), time from completion of therapy, presence and extent of chronic GvHD, and Day 1 Quant Ig. In this exploratory sub-aim, we will also measure HPV-specific total immunoglobulin (total Ig) at Month 24 to better characterize the qualitative aspects of the HPV-specific humoral immune response.^{138,139} We recognize that we may not have sufficient power to test persistence of response to qHPV or 9vHPV vaccine; as such, this aim is exploratory.

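### The seropositivity non-inferiority rule tests the wrong confidence limit, so survivors shown to be worse than healthy recipients can be declared non-inferior

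*Combined protocol and SAP*

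**What the plan says.** Section 8.2.2.1 compares the percentage of survivors seropositive at Month 7 with an age- and sex-matched historical healthy population. It specifies "Two one-sided tests of noninferiority (for each of 2 HPV types"), which "will be conducted for each age-sex group at the 0.025 level (multiplicity adjusted) according to the methods of Miettinen and Nurminen". The next sentence gives the decision rule: survivors are "non-inferior if the lower 95% CI for the difference in percent seropositive between the healthy and cancer population is <5 percentage points". The analysis is headed "Exploratory only; study is not powered for this". It is to be run in both the per-protocol and intention-to-treat samples, with similar analyses for the other vaccine types, and section 8.2.2.1 evaluates the two vaccine cohorts separately.

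Section 8.2.2.4 carries the same rule, with the same 5-point threshold, to Month 24: persistence is "non-inferior in cancer survivors if the lower 95% CI for the difference in percent seropositivity between the healthy and cancer population is less than" that threshold.

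The GMT rules run the right way. In section 8.2.2.1 the lower limit of the cancer-to-healthy ratio must exceed 0.5; in section 8.2.2.4 it must be at least 50%.

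**The concern.** Non-inferiority has to be demonstrated: the confidence interval must exclude a deficit as large as the margin. The written rule asks only that the interval not lie wholly beyond the margin, so failing to prove inferiority becomes a finding of non-inferiority.

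Two perverse consequences follow. A smaller stratum gives a wider interval, which makes the claim easier. A stricter multiplicity adjustment also widens the interval and makes the claim easier, the reverse of its purpose.

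At stake is a false statement that survivors seroconvert like healthy recipients, repeated across HPV types, age-sex strata, analysis samples and both vaccine cohorts. The abstract presents the study as the evidence base for vaccination recommendations in survivors.

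**Working it through.** **Inputs from the documents**
- Margin: 5 percentage points (8.2.2.1, 8.2.2.4).
- Level: one-sided 0.025, described as multiplicity adjusted (8.2.2.1). The adjusted value is not given. Section 8.1 uses "Type I error =0.00312 (for an overall Type I error =0.025") for GMT, which matches 0.025/8 = 0.003125, so this serves as the stricter variant.
- Method: Miettinen-Nurminen.
- Planned qHPV stratum sizes: 72 to 82 (8.1).

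**Assumptions.** The documents give neither the healthy seropositivity rate nor the historical sample size. The main range is a healthy rate of 99% to 99.5% in 800 to 2,500 controls, with 95% as a sensitivity case. The healthy proportion is held at its assumed value.

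**Step 1: the stated level.** Let D = healthy minus cancer, with null hypothesis D ≥ 5 points. At D = 5 in large samples:
- upper limit < 5: probability = α = 0.025, which is the plan's stated level;
- lower limit < 5 (as written): probability = 1 − α = 0.975, or 0.997 at α = 0.003125.

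**Step 2: the other subtraction order.** For cancer minus healthy, the correct condition is a lower limit above −5. The written condition, a lower limit below +5, fails only if survivors are shown to be more than 5 points better. If healthy seropositivity is 95% or more, the difference cannot exceed 5 points, so the rule can never fail.

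**Step 3: finite samples.** The score statistic at the margin is

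z = (p̂h − p̂c − 0.05) / √{[p̃h(1 − p̃h)/nh + p̃c(1 − p̃c)/nc] × N/(N − 1)},

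where p̃h and p̃c are the maximum-likelihood estimates under p̃h − p̃c = 0.05 and N = nh + nc. The written rule is met when z < z(1−α); the corrected rule when z < −z(1−α). Binomial probabilities over all survivor counts, with nc = 72 and α = 0.025, give the same results across 800 to 2,500 controls:

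| | Healthy 95% | Healthy 99% | Healthy 99.5% |
|---|---|---|---|
| Fewest seropositive that pass, written | 60/72 | 64/72 | 65/72 |
| Fewest that pass, corrected | 70/72 | 72/72 | 72/72 |
| Written rule passes, true deficit 5 points | 0.975 | 0.972 | 0.956 |
| Same, 7.5 points | 0.891 | 0.844 | 0.783 |
| Same, 10 points | 0.721 | 0.605 | 0.511 |
| Same, 15 points | 0.295 | 0.166 | 0.113 |
| Corrected rule passes, 5 points | 0.021 | 0.012 | 0.017 |

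At 10 points the corrected rule passes with probability below 0.001 in every column.

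**Step 4: two single results** against 990/1,000 healthy:
- 66/72 (91.7%): D = 7.3 points, 95% CI 2.8 to 16.0.
- 64/72 (88.9%): D = 10.1 points, 95% CI 4.7 to 19.4.

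In both, survivors are significantly worse (lower limit above 0) and the observed deficit exceeds the margin. Both pass as written because the lower limit is below 5. Both fail the corrected rule.

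**Step 5: the perverse direction.** With healthy rates of 99% and 99.5%:
- Tightening α to 0.003125 at nc = 72 raises the false-claim probability at a 10-point deficit to 0.735 and 0.779.
- Shrinking the stratum to 44 at α = 0.025 raises it to 0.646 and 0.686. The 44 is illustrative: 200 further patients split equally over four strata, with section 8.1's 96% seronegative and 92% completion, give 200/4 × 0.96 × 0.92 = 44.2.

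**The case against.** The strongest reply is that little depends on this sentence. The analysis is marked exploratory and unpowered, GMT is named as the primary outcome of interest, the sample size rests on GMT, and the GMT rules are correctly oriented. The sentence before the faulty one calls for one-sided non-inferiority tests at 0.025, which with a 5-point margin is the right test, so the rule may be a slip that a careful analyst would correct. The rule also does not pass everything: in the main range, a true 15-point deficit passes only 11% to 17% of the time. Finally, the sizes rest on assumed healthy rates and control numbers.

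Most of this stands, but it limits the consequence and does not make the rule valid. The exploratory label does not help a formal pass/fail verdict whose error runs the wrong way; low power should make non-inferiority harder to claim. Section 7.2 also lists seropositivity among the Aim 2 primary endpoints. The test and the decision rule now contradict each other, nothing elsewhere resolves them, and a programmer following the explicit rule would implement the wrong one. The large-sample error of 0.975 needs no assumed healthy rate.

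One further point about the remedy is fair: if healthy rates are 99% or more and α is 0.003125, even 72/72 or 82/82 would not pass the corrected rule.

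**Conclusion.** The concern holds. The rule is wrong under either subtraction order, at Month 7 and at Month 24, and it contradicts the one-sided 0.025 test stated beside it. At a true deficit equal to the margin it claims non-inferiority with probability 0.975 in large samples.

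Over a wider set of assumptions (healthy rate 95% to 99.5%, 100 to 1,000 controls, strata of 72 and 82, both α levels), the probability of a non-inferiority claim is 0.92 to 1.00 at a 5-point deficit, 0.36 to 0.98 at 10 points and 0.05 to 0.82 at 15 points. The corrected rule gives at most 0.021 at 5 points and at most 0.001 at 10. These finite-sample figures depend on the assumed control data; the direction of the error does not. The GMT conclusions are unaffected.

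**What to change.** Replace the decision sentence in sections 8.2.2.1 and 8.2.2.4 with: *Seropositivity is non-inferior if the upper multiplicity-adjusted confidence limit for (healthy minus cancer) percent seropositive is below 5 percentage points.* Equivalently, the lower limit for (cancer minus healthy) must exceed −5. Keep the Miettinen-Nurminen method.

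In the same edit, state the per-comparison level, because section 8.2.2.1 does not say whether 0.025 is before or after adjustment and the choice decides whether the criterion can be met.

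The change needs no new data, patients or design work. Its real cost is that the valid criterion is demanding: over the wider range of assumptions above, power at true equality in strata of 72 to 82 is 0 to 0.70, and in some settings a stratum with every survivor seropositive would still fail. That agrees with the plan's own statement that it is not powered here. If the adjusted criterion cannot be met, report the difference and its interval without a pass/fail verdict.

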8.2.2.2. Identify clinical/host factors influencing immunogenicity in cancer survivors

Subjects whose GMT at Month 7 is less than ½ of the mean GMT of the corresponding age-sex matched health population will be classified as having lowered immunogenicity. Logistic regression will be used to identify significant predictors of lowered immunogenicity. Potential predictors include sex, primary diagnosis, current age, age at diagnosis/HCT, prior therapy (all therapeutic exposures, including cumulative doses of all immunosuppressive agents), intensity of therapy (conventional therapy vs. HCT), time from completion of therapy, presence/extent of chronic GvHD, dose/duration of immunosuppressive agents post-HCT, and Day 1 Quant Ig. This analysis will be conducted for HPV-16 and -18. At Type I error=0.5,

312 subjects will achieve 80% power to detect odds ratios of 2.0 to 3.2 depending on the hypothesized and true proportions of subjects with lowered immunogenicity (Table 8) or a dichotomized covariate with 50% of the sample in each group.

Table 8. Proportion of Subjects with Lowered Immunogenicity and Associated Odds Ratios

P0	P1	OR
0.05	0.143	3.18
0.1	0.215	2.47
0.2	0.34	2.06
0.3	0.453	1.93
0.4	0.558	1.89
0.5	0.656	1.91
0.6	0.748	1.98

P0 = Hypothesized proportion of subjects with lowered immunogenicity

P1 = True proportion of subjects with lowered immunogenicity

OR = Odds Ratio

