8.2.2. Aim 2 (Vaccine Evaluation)

8.2.2.1. Determine immunogenicity of qHPV and 9vHPV vaccine 1 month following the third and final vaccine dose

The primary analytic approach will be per-protocol (PP)³⁰ analysis; intention to treat analysis will also be conducted. The evaluation will be completed separately for the qHPV and 9vHPV cohorts. The sample size is powered to determine whether vaccine-induced anti-HPV-16 and -18 neutralizing antibody response in cancer survivors is comparable to the age- and sex-matched general population (Table 7); PP immunogenicity population includes participants who are seronegative for the oncogenic vaccine components of primary interest (HPV-16, -18) on Day 1, complete all three vaccine doses within the protocol-specified time frames, and have immunogenicity data available at the time of analysis. Each vaccine component will be analyzed separately, and we will adjust for intensity of treatment. Anti-HPV-6 and -11 (and in the 9vHPV cohort, Anti-HPV-31, -33, -45, -52, and -58) response will also be explored. The primary outcome of interest is GMT. We will also assess seropositivity rates among cancer survivors. Seropositivity (binary variable) is defined as: qHPV cohort: Anti-HPV-6, -11, -16, and -18 titer ≥ 20 , 16, 20, and 24 mMU/ml respectively;³⁰ 9vHPV cohort: Anti-HPV-6, -11, -16, -18, -31, -33, -45, -52, and -58 titer ≥ 30 , 16, 20, 24, 10, 8, 8, 8, and 8 mMU/ml, respectively.⁶⁹

Outcome measure (GMT): Using the historical healthy population for qHPV²⁸ and 9vHPV⁶⁹ respectively, a multiplicity-adjusted 95% 2-sided confidence intervals for the ratio of mean GMT for HPV-16 and -18 in the cancer and healthy population will be computed. If the lower 95% limit is greater than 0.5, immunogenicity in cancer survivors will be considered non-inferior.³⁰

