8.2.2.3. Determine the safety/tolerability of the qHPV and 9vHPV vaccine in cancer survivors

In the IT sample, the number of vaccine-associated AE within 7 (for 9vHPV) or 14 (for qHPV) days of each dose will be compared to those reported for the age- and sex-matched general population: % of subjects with injection site AEs (e.g., pain, erythema), % of subjects with systemic AEs (e.g., fever, syncope, headache, hives, rashes, diarrhea), % of subjects with serious AEs (e.g., life-threatening, result in persistent disability or death). Overall cohort: % of subjects who discontinue vaccine related to AE. AEs will be summarized descriptively as frequencies and percentages by type (injection site, systemic, serious), by vaccine dose (i.e., #1, #2, #3), and across all vaccine doses. Chi-square and exact tests will be used for comparison depending on the rarity of events. Our smallest PP subsample of 72 young females will provide 80% power to detect a difference of 0.0485 in AE rates if true rate=0.01, and a difference of 0.1068 if the true rate=0.85. For the largest PP subsample of 82 young males, the corresponding detectable differences are 0.0415 and 0.1021. For the entire PP sample of 312, the corresponding differences are 0.0189 and 0.0534. Type I error=.05 is assumed for each comparison.

8.2.2.4. (Exploratory sub-aim): Evaluate the persistence of antibody response at 2 years post vaccine initiation and identify clinical/host factors influencing response persistence.

Outcome measure (GMT): We will calculate mean GMT and 2-sided 95% CI for HPV-16 and -18 at Month 24 following vaccine initiation for PP subjects and compare them to age-, sex-, and time-matched means in the historical healthy population.²⁸ Cancer survivors will be considered to have non-inferior persistence of antibody response to a subtype at a time point if the lower 95% confidence limit for the ratio of GMT in cancer survivors to historical healthy population is $\geq 50\%$.³⁰

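### Aim 2b's power statement is wrong as printed (Type I error 0.5, odds-ratio floor 2.0, superseded N=312, pooling unstated), and its only model cuts titre at half the healthy GMT: correct it and add a log-titre model

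*Combined protocol and SAP*

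**What the plan says.** Section 8.2.2.2 labels a subject as having lowered immunogenicity when the Month 7 titre is under half the mean GMT of the age- and sex-matched healthy population. The one model named is: "Logistic regression will be used to identify significant predictors of lowered immunogenicity". It would be run for HPV-16 and HPV-18.

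The power statement opens "At Type I error=0.5" and continues "312 subjects will achieve 80% power to detect odds ratios of 2.0 to 3.2", with Table 8 listing the effects "or a dichotomized covariate with 50% of the sample in each group". Table 8's odds ratios are 3.18, 2.47, 2.06, 1.93, 1.89, 1.91 and 1.98.

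Three other places bear on this:
- Section 8.2.2.3, the next section, states "Type I error=.05 is assumed for each comparison".
- Section 8.1 derives 312 as the original qHPV per-protocol target ("92% (n=312) will complete all 3 doses"). It then reports that qHPV enrolment ended at 254 and plans an additional 200 patients on 9vHPV.
- Section 8.2.2.1 says "The primary outcome of interest is GMT" and "The evaluation will be completed separately for the qHPV and 9vHPV cohorts". Section 8.2.2.2 does not say whether that separation applies to its regression.

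**The concern.** Aim 2b is a stated aim, and Section 8.2.2.2 is where the plan looks for the treatment-related differences that Hypothesis 2 predicts. A reader cannot tell from it which error rate applies, which sample the 80% describes, or whether the two vaccine cohorts are combined. Leaving pooling open also allows that choice to be made after results are known.

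The modelling question is separate. Titre is the primary outcome, yet the search for predictors uses only which side of the cut each titre falls on. A patient just under half the healthy mean counts the same as one with almost no response. The responder model does fit the aim of finding inadequate responders (Section 2.10.2). As the only model, it could miss a moderate fall spread across a whole exposed group.

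**Working it through.** **1. Reproducing Table 8.** Inputs: N=312, so n=156 per covariate group, and the printed P0 and P1. Formula (two proportions, pooled null variance):

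power = Φ{[(P1−P0) − z(α/2)·SE0] / SE1}, where SE0 = √[2p̄(1−p̄)/n] and SE1 = √[P0(1−P0)/n + P1(1−P1)/n].

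Row P0=0.4, P1=0.558: p̄=0.479, SE0=0.0566, SE1=0.0559.
- α=0.05 two-sided: (0.158 − 1.960×0.0566)/0.0559 = 0.84, power 80%.
- α=0.5 two-sided: (0.158 − 0.674×0.0566)/0.0559 = 2.15, power 98.4%.

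Over all seven rows, power is 79.7–80.1% at two-sided 0.05, 87.5–87.8% at one-sided 0.05 and 98.4% at 0.5. The α that gives exactly 80% is 0.0497–0.0511. Table 8 is therefore sound at N=312, and the 0.5 is a misprint. Table 8's odds ratios run from 1.89 to 3.18, with 1.89, 1.91, 1.93 and 1.98 below the text's floor of 2.0.

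**2. Current sample sizes.** Same formula, two-sided 0.05, 50/50 covariate:

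| Analysis | N | Power at Table 8 effects | OR detectable at 80% |
|---|---|---|---|
| As printed | 312 | 80% | 1.89–3.18 |
| qHPV alone | 254 | 71% | 2.03–3.52 |
| 9vHPV alone | 200 | 61% | 2.22–4.01 |
| Pooled | 454 | 92% | 1.70–2.69 |

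These use enrolled or planned numbers. If Section 8.1's rates (96% seronegative, 92% completing three doses; product 0.883) are assumed to hold, N is about 224, 177 and 401, and power is 66%, 56% and 89%.

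**3. Information lost by the cut.** Relative to linear regression on log titre, loss = 1 − f(c)²·variance/[p(1−p)]. Here f is the log-titre density, c the cut and p the proportion below it. Survivors are assumed to resemble the healthy population in Table 7. The documents do not give the log-titre distribution, so Table 7's means are read both ways.

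Example, younger females, HPV-16, normal log titres: SD/mean = 5585.26/4918.5 = 1.136.
- Mean read as arithmetic: log SD = √ln(1+1.136²) = 0.910. The cut lies at ln(0.5)/0.910 + 0.910/2 = −0.307 SD, p=0.38, loss 38%.
- Mean read as geometric: log SD 0.745, cut at −0.931 SD, p=0.176, loss 54%.

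Over the eight Table 7 cells (arithmetic / geometric reading):
- normal: 38–40% / 53–55%
- logistic-shaped: 22–26% / 55–59%
- t with 5 df: 10–17% / 55–60%

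**4. Power of the two models.** Simulation for HPV-18, four strata weighted 72/77/82/81, single factor, with unexposed survivors set equal to healthy. Both tests reject 4.7–5.3% of the time under no effect.

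Uniform 30% fall (an assumed effect), 50/50, N=254, log titre vs cut:

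| Shape | Arithmetic | Geometric |
|---|---|---|
| Normal | 87 vs 69% | 96 vs 79% |
| Logistic-shaped | 86 vs 79% | 97 vs 82% |
| t, 5 df | 87 vs 86% | 96 vs 84% |

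When only 15–40% of exposed patients respond poorly (titre 75–90% lower, normal log titres; N=200, 254 and 454), the log-titre model's gain in percentage points is:
- arithmetic, 50/50: 0 to +42
- arithmetic, 19% exposed: +2 to +33
- geometric, 50/50: 0 to +20
- geometric, 19% exposed: −2 to +11 (2 points or less in 12 of 18 cells)

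**5. Titres below the assay limit.** Taking the HPV-18 cutoff of 24 mMU/ml as the limit (assumed), under 1% fall below it if survivors resemble the healthy. With titres 90% lower, 9–47% (arithmetic) or 1–25% (geometric) do, depending on stratum. Substituting half the cutoff moved power by at most 0.5 points.

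**The case against.** Two of the four power faults are editorial. Table 8 is right, and the misprinted error rate and rounded floor change no analysis. That stands. The exact α recovered also depends on the test: at N=312, unpooled variance gives 0.047–0.048 and a Wald log-odds test 0.052–0.068. All of these are close to 0.05 and far from 0.5.

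The N and pooling faults come down to one missing sentence and an outdated number, and under pooling the printed 80% would be conservative. That also stands. But the authors must settle it, because power moves by 21 to 31 points with the answer.

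On the model, a responder cut tied to the trial's own 0.5 non-inferiority limit is a legitimate choice, which is why it should stay. Section 8.2.2.1 also adjusts the GMT evaluation for treatment intensity. That covers one factor and is not a predictor model for those listed in Section 8.2.2.2. The benefit of a log-titre model does rest on an unstated distribution and assumed effects, and in some cases it is nil.

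A second model adds flexibility. Month 7 data from 133 qHPV patients had already been analysed in January 2016, so the model should be identified as a later addition.

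**Conclusion.** The concern holds. The power statement is wrong as printed on error rate, odds-ratio floor and sample size, and it is silent on pooling. The first two are wording corrections. The last two change what the section can detect: 71% or 61% power in separate cohorts, 92% pooled, and lower after attrition. These figures assume a single evenly split factor and Table 8's effects.

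That the cut discards information is certain under the three distributions examined, but the amount is not: 10–60% across shapes and readings of Table 7. The log-titre model helps most when titres fall moderately across an exposed group. It may add nothing with heavy tails or when only a subset responds poorly. The two models are complementary, and this is a change the plan should make.

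**What to change.** In Section 8.2.2.2:
- Print a two-sided Type I error of 0.05 and an odds-ratio range of 1.89–3.18 for Table 8 as it stands.
- Restate Table 8 for the actual evaluable N. Relabel P0 and P1 as the proportions in the two covariate groups, which is what was computed.
- State whether the cohorts are pooled, with a vaccine-cohort term, or analysed separately.
- Keep the half-GMT logistic model for identifying inadequate responders. Beside it, add a linear regression of log(titre / age-, sex- and vaccine-matched healthy GMT) on the listed predictors, with robust standard errors.
- State a rule for titres below the assay limit, for example half the limit with a censored-regression check.
- Say which question each model answers, and that the second was added after the interim look.

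Optional, not a correction: the 50/50 split is a disclosed planning case, but rows for an HCT share near 19% would inform that comparison. The share comes from Table 2's potentially eligible patients, with a site range of 8.3–45.8%. Power at Table 8's effects is then 48–61% (N=254), 39–53% (200) or 74–81% (454).

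The cost is SAP wording and one extra model on data already collected. The downsides are a second set of estimates to report and a less favourable printed power if the cohorts stay separate.
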